Note #1: We will review baseline sociodemographic, psychiatric, medical history variables, HCV infection and HIV illness stage to determine whether there are significant differences between treatment groups on any relevant measure. If so, each measure will be studied in terms of their relationship to treatment outcome. If related to outcome, they will be entered as covariates in all outcome analyses. To distinguish between depression and fatigue, a depression measure (BDI [67]) will be used as a covariate in all analyses. In addition to standard scoring, the depression measures (BDI and HAM-D [67]) will be adjusted and scores prorated to exclude the fatigue items.

Missing Data. The pattern and distribution of missing data will be examined, and recourse taken to assess randomness and correlates as described in Cohen and Cohen [87, Chapter 7]. Assuming it is randomly distributed, appropriate estimates of missing values will be generated and used in analyses. For AIM 2 the examination of the secondary outcomes across the treatment period (i.e. BADS and EROS Scales), we will be using Linear Mixed Models for analyses. In the presence of missing data, Mixed Models uses all data, estimates parameters and test hypotheses about them but do not impute missing values [88], and Mixed Models can reduce bias due to dropouts [89]. For dichotomous outcomes, secondary

analyses will be performed that use alternative methods of imputation (e.g. last observation brought forward).³

Attrition. We will deal with dropouts in 3 ways: excluding dropouts, counting dropouts as failures, and finally counting dropouts as responders, providing an idea of all possible outcomes are. As noted above, we will use Linear Mixed Models for analyses where appropriate, which can reduce bias due to dropouts.

Data Transformation. We will check all variables in terms of univariate and bivariate distributions to make sure any data analytic method we use appropriately reflects the relationship between the variables-- e.g. we will use nonlinear transformations and polynomial regression as necessary.

Definition of primary dependent variables:

Work: paid employment: 4+ hours/week including stipend jobs; volunteer work; Increased work hours: at least 20% increase with a minimum increase of 4 hours/week.

Training: Includes enrollment in GED classes, degree and vocational programs, computer classes, unpaid or stipend internships.

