5.8.3: Analytic Strategies. (End points are final study visit and 3-month follow-up visit)

Specific Aim 1: to determine whether more patients in BA-PEP (N=70) return to work or start training compared to SC patients (N=70).

Hypothesis 1: Our primary outcome measure is success in work/training goal attainment using a modified GAS score; we hypothesize that 60% of BA-PEP patients will succeed as compared to 25% of SC patients. BA-PEP will significantly promote success in work goal attainment as compared to SC.

Analysis Plan: The effect of BA-PEP on the primary outcome (work goal attainment) will be examined using a logistic regression (PROC LOGISTIC in SAS[®]) adjusted for appropriate covariates (e.g., stratification variable, depression measure).

Specific Aim 2: Determine whether secondary outcomes, as measured from baseline to the end of treatment, differentiate between BA-PEP and SC. These include the Behavioral Activation Depression Scale, the Environmental Reward Observation Scale (EROS), Endicott Quality of Life, Role Function scale, and Mastery.

Hypothesis 2: Over time, the BA-PEP patients will show significantly more improvement compared to SC patients.

Analysis Plan: Hypothesis 2 will be analyzed using longitudinal mixed effect models (PROC GLIMMIX in SAS[®]) with main effect of time, treatment and interaction between treatment and time effect. The within subjects repeated measure across time will be the baseline session, session 4, and session 8 [end of treatment] assessments for the BADS Scales and the EROS, and the between subjects factor will be the two treatments (i.e. SC and BA-PEP counseling). Demographic measures and other characteristics that are significantly different between the two treatment groups at baseline, will be included as covariates. The main focus of the analysis will be on the interaction term of treatment and time, which addresses treatment group response over time. If the interaction term of treatment and time is found to be significant, we will test the contrast between treatment groups at session 8 [end of treatment].

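### The Aim 2 follow-up contrast at session 8 is not adjusted for the scale's own baseline, which costs precision and lets it disagree with the interaction test that precedes it

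*SAP*

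**What the plan says.** SAP 5.8.3, Specific Aim 2, states the hypothesis as "Over time, the BA-PEP patients will show significantly more improvement compared to SC patients". The model is fitted "with main effect of time, treatment and interaction between treatment and time effect", and for the BADS scales and the EROS "The within subjects repeated measure across time will be the baseline session, session 4, and session 8 [end of treatment] assessments". Baseline is therefore an outcome, not a covariate.

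The principal test is stated clearly: "The main focus of the analysis will be on the interaction term of treatment and time, which addresses treatment group response over time". Only if that term is significant does the second step follow: "we will test the contrast between treatment groups at session 8 [end of treatment"]. The step is not defined as a difference in change, and it names no baseline score.

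Two covariate provisions bear on this. The Aim 2 plan says "Demographic measures and other characteristics that are significantly different between the two treatment groups at baseline, will be included as covariates". Note #1 in 5.8 says "a depression measure (BDI [67]) will be used as a covariate in all analyses".

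**The concern.** With time, treatment and their interaction all in the model, each arm has a free mean at every visit, baseline included. The session-8 contrast from such a model compares levels. The interaction that opens the gate compares change. When the arms start apart by chance, the two steps answer different questions and can give different answers, and the plan has no rule for that case.

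Neither covariate provision reliably closes the gap. BDI is not the baseline BADS or EROS score. The significance rule would act on the baseline score in about 5% of trials per scale and leave smaller gaps unadjusted. When it did act, the same score would be both a covariate and the first outcome.

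At stake is the precision of the only end-of-treatment comparison that the plan names for these scales.

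**Working it through.** **Inputs.** From the SAP's power paragraph for Hypothesis 2: 70 per arm, three measures, two-sided .05, correlation rho = .30, and effect size/power of .45/80%, .48/85%, .52/90%, .58/95%. Assumed here: equal variances, the same correlation between all visits, complete data, no other covariates, effects in session-8 SD units, normal approximation. Power = Phi(d/SE - 1.96).

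**1. The SAP's own figures.** The SAP does not name its method. A baseline-adjusted session-8 comparison has SE = sqrt(2(1 - .30²)/70) = 0.161. At d = .45: .45/0.161 = 2.79, less 1.96 = 0.83, power 79.7%. The four effect sizes give 79.7 / 84.5 / 89.7 / 94.9%, which matches 80/85/90/95%. Of the variants tried (including raw session 8, change, averages over visits and the two-degree-of-freedom interaction), only this one reproduces all four within 2 points.

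**2. The contrast as written.** SE = sqrt(2/70) = 0.169. At d = .45: 2.66 - 1.96 = 0.70, power 75.9%. The four effect sizes give 75.9 / 81.1 / 86.8 / 92.9%.

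**3. A change-from-baseline contrast.** SE = sqrt(2 × 2(1 - .30)/70) = 0.200. At d = .45: 2.25 - 1.96 = 0.29, power 61.4%.

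**4. A chance baseline gap b.** Given b, the expected shift is:
- raw session-8 contrast: rho × b = 0.30b
- change contrast: (rho - 1) × b = -0.70b
- baseline-adjusted contrast: 0

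Take b = 1.96 × 0.169 = 0.33 SD, which chance exceeds in 5% of trials per scale (2.5% in each direction). The raw contrast shifts by 0.30 × 0.33 = 0.10 SD and the change contrast by 0.70 × 0.33 = 0.23 SD. If the gap runs against BA-PEP and the true effect is .45, the raw contrast has mean .45 - 0.099 = 0.351 and conditional SD 0.161, and it must exceed 0.331. Power = Phi((0.351 - 0.331)/0.161) = about 55%. The adjusted contrast stays at 80%.

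**5. The sequence with its gate.** Simulation of the arm differences with known covariance and rho = .30:

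| | No effect | Linear effect reaching .45 |
|---|---|---|
| Interaction significant | 5.0% | 50.9% |
| Interaction and raw session-8 contrast | 1.15% | 45.5% |
| Interaction and baseline-adjusted contrast | 1.7% | 48.9% |

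The last row keeps the interaction test as written and changes only the contrast. Under the linear effect, the raw contrast fails after a significant interaction in (50.9 - 45.5)/50.9 = about 10.6% of those trials; the adjusted one fails in (50.9 - 48.9)/50.9 = about 4%.

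**6. Higher correlations.** Values of .50 and .70 are not in the SAP. Under them the adjusted contrast would have 86.7% and 96.1% power at d = .45, against 75.9% raw. With the 0.33 SD gap against BA-PEP, raw power would be about 37% and 17%.

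**The case against.** The strongest reply is that the interaction, not this contrast, carries Hypothesis 2. It uses baseline, compares change and is named as the main focus. That stands. A reader might infer that Aim 2 never tests improvement; the text does not support this, and the point is confined to the follow-up contrast.

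A reader might also infer that chance imbalance inflates false claims for BA-PEP. Taken alone, with a 0.33 SD gap favouring BA-PEP and no effect, the raw contrast errs in that direction in 7.5% of trials at rho = .30 rather than 2.5%. But the plan does not run it alone. The same gap makes change look worse for BA-PEP, so the gate usually stays shut: a significant interaction plus a contrast favouring BA-PEP occurs in about 0.7% of such trials. Over all randomisations the contrast is unbiased with 5% error. The inflation reading fails. The power loss when the gap runs the other way does survive the gate, at about 55%.

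Three further replies have some force:
- A 0.33 SD gap lies at the threshold of the SAP's significance rule, so larger gaps might bring the baseline score in as a covariate. Smaller ones would not.
- BDI may absorb part of the prognostic difference. How much is unknown.
- An endpoint contrast after a significant interaction is a recognised approach, and at rho = .30 the average gain from adjustment is modest.

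**Conclusion.** The point holds as a loss of precision in a gated, secondary contrast. As written, the contrast compares session-8 levels without the scale's baseline. At the SAP's correlation of .30 and d = .45 it has about 76% power alone, where the SAP states 80% and baseline adjustment delivers it. Through the gate the difference is about 45% against 49%. In the uncommon case of a 0.33 SD gap against BA-PEP, it is about 55% against 80%. These figures rest on the assumptions listed in the working; a correlation above .30 would enlarge the loss.

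The documents do not support calling this a failure to test Hypothesis 2 or a source of excess false positives. The primary analysis in Aim 1 is untouched. The change is still worth making, because it uses data the trial already collects and brings the contrast into line with the stated power.

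**What to change.** Estimate the session-8 treatment contrast with baseline adjustment, in one of two forms:

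- **Common baseline mean.** Keep the three-visit mixed model but constrain the arms to one baseline mean, with treatment terms only at sessions 4 and 8. The SAP should specify these as explicit indicators. With class variables, deleting the treatment main effect while keeping the full treatment-by-time term merely re-parameterises the same model.
- **Baseline covariate.** Model sessions 4 and 8 as outcomes, with that scale's baseline score as a covariate.

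Define the treatment-effect test to match the chosen model. Under the covariate form it is the joint treatment effect at sessions 4 and 8, since treatment-by-time would then test only whether the effect differs between those two visits. State that adjustment for the analysed scale's baseline always applies, whatever the significance rule for other baseline characteristics finds.

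Do not substitute a simple change-from-baseline contrast: at rho = .30 it has about 61% power and is more sensitive to baseline gaps (0.70 of the gap against 0.30).

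The cost is SAP wording and a revised model and test statement, with no new data or patients.

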Specific Aim 3: To identify predictors of success in goal attainment, including moderator variables such as concurrent Axis I depression, baseline BDI scores, health history and status, substance use history, time since last employed full-time and neuropsychological function. We will also examine mediating variables such as changes in apathy, mastery, coping style, motivation, mood (since starting counseling) and quality of life.

Hypothesis 3: We expect several of these characteristics particularly depression, age, health status and neuropsychological function, to show significant association to successful goal attainment.

Analysis Plan: We will use Logistic Regression (LR) Analysis available in SAS® statistics package (PROC LOGISTIC). This LR procedure will be performed hierarchically within each treatment arm separately, as well as the combined treatments (BA-PEP + SC treatments). The dichotomous dependent outcome measure will be successful goal attainment or not. At the first analysis step, age sex and education and possibly other covariates will be entered into the model, followed by the measures mentioned above using the backward stepping procedure. We will also examine moderator variables by investigating the interaction of treatment arm with each variable listed above. We will examine as mediator variables the changes in apathy, mastery, coping style, motivation, mood, and quality of life from baseline to session 4. Change in baseline to session 4 will be used in order to have a reliable measurement before or closest to obtaining the goal for those that will obtain the goal, since obtaining the goal could also affect these potential mediator variables.

Power Considerations (Power calculations do not include Historical Control data.)

Pilot Data: In our pilot work, we have treated 31 patients with the BA-PEP; 19 (61%) achieved their goals. In the combined modafinil and armodafinil RCTs, about 28% who wished to do so returned to work.

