Hypothesis 1: 60% of BA-PEP treated patients will attain their goal compared to 25% of the SC treated patients. We will enroll 70 patients into each treatment arm (50 who responded to armodafinil and 20 who self-described as fatigued but did not meet fatigue criteria). With expected rates of 60% and 25% goal attainment, a difference of 35%, power is over 95%. Differences as small as 23% can be detected with 80% power, for reasonable percentages of goal attainment in the SC treated patients, e.g., (48% BA-PEP vs. 25% SC), (53% BA-PEP vs. 30% SC), (63% BA-PEP vs. 40% SC).

Hypothesis 2: We predict that the secondary assessments will distinguish between the two treatment groups with BA-PEP patients showing more improvement by the end of the treatment period compared to SC patients. Using power estimates for three repeated measures (baseline session, session 4, and session 8 [end of treatment]), for 70 patients per group, alpha set at $p < .05$ for a two-tailed test and correlation between repeated measures estimated at .30: (Effect size/Power) .45 [medium]/80%, .48/85%, .52 /90%, .58/95%.

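### Aim 3 tests raw baseline-to-session-4 changes as mediators without specifying that each scale's own baseline enters the model, so a prognostic starting level can create or mask a mediator-outcome association

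*SAP*

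**What the plan says.** The Aim 3 analysis plan in SAP section 5.8.3 uses logistic regression on dichotomous goal attainment. On mediators it states: "We will examine as mediator variables the changes in apathy, mastery, coping style, motivation, mood, and quality of life from baseline to session 4". The reason it gives for stopping at session 4 is timing, "since obtaining the goal could also affect these potential mediator variables". That deals with reverse causation and does not bear on starting level.

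On covariates, it states: "At the first analysis step, age sex and education and possibly other covariates will be entered into the model". The predictor list includes "concurrent Axis I depression, baseline BDI scores, health history and status", and Note #1 in section 5.8.2 adds that "a depression measure (BDI [67]) will be used as a covariate in all analyses", without giving a time point. The baseline values of the other five mediators (motivation, mastery, apathy, quality of life and coping style) are not named for any mediator model.

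The only between-visit correlation in the SAP is in the Hypothesis 2 power paragraph: "correlation between repeated measures estimated at .30".

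**The concern.** A change score is the later value minus the baseline, so baseline enters it with a negative sign. If people who start higher on a scale are more (or less) likely to reach their work or training goal, the raw change picks up that relation with its sign reversed, even when movement on the scale plays no part. Conversely, if starting level and session-4 level both help, their contributions to the change score oppose each other and a real effect of the session-4 level can disappear.

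The mediator part of Aim 3 is meant to show which early changes accompany success. With baseline left out, a coefficient for change cannot be separated from a coefficient for starting level.

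**Working it through.** **Inputs from the SAP.** 70 patients per arm; 60% against 25% goal attainment; alpha .05, "for a two-tailed test"; correlation .30. The .30 is given for the Hypothesis 2 assessments. Mastery and quality of life are on both that list and the mediator list; for the other mediators the figure is an assumption, so .70 is shown as well.

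**Assumptions.** Equal SDs at the two visits; odds ratios of 1.3 to 2.0 per SD for a prognostic level; an arm effect on the scale of 0 or .45 SD.

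**1. The plan's own figure.** Hypothesis 2 states effect sizes .45, .48, .52 and .58 for 80, 85, 90 and 95% power. Power = Φ(d × √(70/2) / √v − 1.96), where v is the variance factor.
- Baseline-adjusted, v = 1 − .30² = .91: 79.7, 84.5, 89.7 and 94.9%. All four are reproduced.
- Raw change, v = 2(1 − .30) = 1.40: 61.4, 67.0, 73.9 and 82.6%. None is reproduced.

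Of six variance forms tried, only the baseline-adjusted one matches. This does not prove how the figures were obtained, but they are consistent with baseline adjustment and not with raw change.

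**2. Change and baseline.** In SD units, cov(change, baseline) = .30 − 1 = −.70 and var(change) = 2(1 − .30) = 1.40. The correlation is −.70/√1.40 = −.592, and its square is .35. At correlation .70 it is −.30/√.60 = −.387, squared .15. With unequal SDs at .30, the share is 50% when the session-4 SD is 0.8 of the baseline SD and 22% when it is 1.25.

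**3. False mediator-outcome path.** Logistic simulation, 4,000 trials per case, arm in the model, baseline prognostic, no session-4 effect:

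| Baseline odds ratio per SD | Raw change, correlation .30 | Raw change, correlation .70 |
|---|---|---|
| 1.3 | 12.5% | 8.5% |
| 1.5 | 22.7% | 12.7% |
| 2.0 | 55.1% | 26.5% |

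With baseline added, the rate is 4 to 5.5%. A repeat with 2,000 trials per case gave 12, 24 and 54% at .30, and 9, 12 and 27% at .70. In that repeat at .30, 98 to 100% of the significant results had reversed sign.

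**4. Both paths required** (the arm moves the scale, and change is associated with success), correlation .30:
- No arm effect on the scale: 0.9% at odds ratio 1.5 and 3.0% at 2.0.
- Arm effect .45 SD: about 14 to 17% at 1.5 (two simulations) and about 33% at 2.0. In a separate simulation with the same arm effect and baseline log odds ratios of 0.2 to 0.7, the baseline-adjusted models gave 3 to 4%.

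**5. Masking.** If the log odds contain a × session-4 level + c × baseline, then cov(change, a·S4 + c·B) = (a − c)(1 − ρ), which is zero when a = c. With both odds ratios at 1.5, simulated power is 4.5% for raw change and 52% with baseline added.

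**6. Where there is no problem.** In a simulation with 1,500 trials per case, if neither level matters the rejection rate is 4.9% raw and 5.3% adjusted. If success depends on the difference itself (log odds ratio .5 at session 4 and −.5 at baseline), the mean coefficient is .524 raw and .528 adjusted.

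**The case against.** The strongest reply is that the plan never writes a mediator model out in full. It leaves room for further covariates, puts the BDI in every analysis, and asks about change, for which a change score is the natural variable. Parts of this stand, and they limit what can be claimed.

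- A reader might infer that the change score is mostly baseline in reverse. At .30 with equal SDs, 35% of its variance is baseline, and it correlates just as strongly (+.592) with session 4.
- A reader might infer that baseline is excluded. The plan does not specify it, which is different, and mood is at least partly covered. That cover does not carry over: with a BDI-like covariate correlated .5 (assumed) with a scale's baseline, the false rate is still 17% at odds ratio 1.5 and 35% at 2.0. An optional, unnamed covariate is no safeguard either.
- A reader might take the 12 to 55% as the rate of falsely declared mediators. It is the rate for one path, and requiring both lowers it (step 4).
- A reader might infer that improvement will wrongly appear to lead to work. In the simulated case, where a higher baseline favours success, the two paths have opposite signs. Both were significant in the direction of improvement leading to success in 0.1% of trials or fewer. A false favourable path needs a worse start to predict success, and the SAP does not say this.
- Hypothesis 3 expects depression and health status, among others, to relate to success. It does not say so for baseline apathy, mastery, motivation or coping style, so those odds ratios are assumptions.

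The omission for the five non-mood scales still stands. Section 5.8.2 admits covariates that differ between arms and relate to outcome, and a baseline can confound a change score without any imbalance between arms.

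**Conclusion.** The point holds in a conditional form. The plan fixes raw changes as mediators and does not specify each scale's own baseline. If starting level is related to success at odds ratio 1.3 to 2.0 per SD, the mediator-outcome test is significant in about 12 to 55% of trials at correlation .30, or about 9 to 27% at .70, instead of 5%, with the sign reversed. With both paths required, the figure is about 1 to 3% if the arm does not move the scale and about 14 to 33% (odds ratio 1.5 to 2.0) if it does by .45 SD. A real session-4 effect can be hidden, with about 5% against 52% power in the case shown.

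These sizes rest on equal SDs, on the assumed odds ratios, and on extending the .30 beyond mastery and quality of life. The documents do not support saying that mediators will be wrongly found or missed, only that they can be. Aims 1 and 2 are not touched.

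**What to change.** In the Aim 3 analysis plan of SAP section 5.8.3, state that each mediator model includes the baseline value of the same scale alongside its change score. Using the session-4 value with baseline as a covariate gives the same mediator coefficient. Apply this to both the treatment-to-mediator and the mediator-to-outcome model. In the first, randomisation already guards against bias and the gain is precision: at .30 the variance factor falls from 1.40 to .91. For mood, say that the baseline of the scale actually used enters, and give the time point of the BDI covariate.

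The cost is a sentence of SAP wording and one extra term per model. The change scores already require the baseline data, and little is lost where the adjustment proves unnecessary (step 6).

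### Aim 3 tests session-4 changes only for association with success; no stated analysis tests whether BA-PEP alters them, so a mediator cannot be told from a prognostic correlate

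*SAP*

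**What the plan says.** SAP 5.8.3, Specific Aim 3, separates moderators from mediators. On the mediators the Analysis Plan says: "We will examine as mediator variables the changes in apathy, mastery, coping style, motivation, mood, and quality of life from baseline to session 4". It justifies session 4 by noting that reaching the goal could itself change these measures.

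The one method named for the aim is logistic regression (PROC LOGISTIC). Its outcome is fixed: "The dichotomous dependent outcome measure will be successful goal attainment or not". On how it is run: "This LR procedure will be performed hierarchically within each treatment arm separately, as well as the combined treatments (BA-PEP + SC treatments". Treatment arm is mentioned as a model term only for moderators: "We will also examine moderator variables by investigating the interaction of treatment arm with each variable listed above".

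Between-arm comparisons of scales are in Specific Aim 2. Of its outcomes the SAP says: "These include the Behavioral Activation Depression Scale, the Environmental Reward Observation Scale (EROS), Endicott Quality of Life, Role Function scale, and Mastery". The repeated measures are spelled out as baseline, "session 4, and session 8 [end of treatment] assessments for the BADS Scales and the EROS". If the treatment-by-time interaction is significant, "we will test the contrast between treatment groups at session 8 [end of treatment"].

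**The concern.** A mediator must be changed by the treatment, and that change must carry part of the treatment's effect to the outcome. The stated regression addresses only the link from the change to success. The link from arm to the change has no stated model, and no indirect effect or criterion for mediation is given.

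The plan cannot therefore distinguish two cases: a change that BA-PEP produces and that helps patients reach their goal, and a change that occurs equally in both arms and simply marks patients who were going to do well. The second is a prognostic correlate. Reporting it as the way BA-PEP works would be wrong, and nothing in the stated analysis would reveal the mistake.

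**Working it through.** **1. Which stated analysis could test arm on mediator?**

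- Within-arm logistic models: none can, because treatment is constant within an arm.
- Combined logistic model: success is the outcome, so even with arm added it does not test whether arm changes the mediator. Arm is not stated as a term.
- Moderator interactions: these ask whether a variable's relation to success differs by arm, which is a different question.
- Aim 2: of the six candidates, only mastery and quality of life are on its list. Its time points are spelled out only for BADS and EROS, and its stated contrast is at session 8, whereas the mediator is the change to session 4.

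So no between-arm test of a session-4 mediator change is stated for any of the six.

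**2. Inputs for an illustration.** From SAP Power Considerations: 70 per arm and 60% versus 25% success. Two-sided alpha 0.05 is stated for Hypothesis 2 and assumed here. The odds ratio (OR) per SD and the arm effect on the mediator are assumptions, because the SAP gives neither.

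**3. The plan's own figure.** The SAP gives no figure for mediation. Its Hypothesis 1 power reproduces with the pooled two-proportion formula:

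z = [0.35 − 1.96·√(2 × 0.425 × 0.575 / 70)] / √[(0.60 × 0.40 + 0.25 × 0.75) / 70] = (0.35 − 0.1638) / 0.0781 = 2.38, so power is 99.1% (stated: over 95%).

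The 23-point differences give 81.4% (48 vs 25), 79.5% (53 vs 30) and 78.3% (63 vs 40), against a stated 80%. The design inputs are sound; none of these figures bears on mediation.

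**4. A change that BA-PEP does not affect.** Simulation, 3000 trials per row, one candidate, arm in the model:

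| OR per SD (assumed) | Change associated with success | Arm effect on the change also significant |
|---|---|---|
| 1.5 | 57–58% | 2.6–2.9% |
| 1.8 | 85% | 4.2% |
| 2.0 | 94% | 5.0% |
| 2.2 | 98% | 5.2% |
| 2.5 | 99% | 5.3% |

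The last column is roughly alpha times the middle one: 0.05 × 0.58 = 0.029 and 0.05 × 0.85 = 0.043. Across repeated runs it lies at about 2–5%. For OR 1.5/1.8/2.2, the within-arm models find the association in 27/50/72% of trials (SC) and 34/60/84% (BA-PEP).

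**5. If arm is left out of the combined model.** Take a change that BA-PEP shifts by 0.5 SD but that has no effect on success. It is flagged in 17.5% of trials without arm and in 4.5% with arm. Arm drives both the change and success, which creates the association.

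**6. What a joint requirement costs.** For a true mediator (arm effect 0.5 SD, OR 2.0), both steps are significant in 78% of trials. For the arm step alone, unadjusted, power is about Φ(d·√(70/2) − 1.96). At d = 0.3 this is Φ(1.775 − 1.96) = Φ(−0.185), about 42% with the t-test. At d = 0.4 it is Φ(2.366 − 1.96) = Φ(0.406), about 65%.

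**The case against.** **No decision rule is stated.** A reader might infer that the plan calls any change that predicts success a mediator. The SAP does not say so. It says the changes will be examined as mediators and stops there, and the protocol, which was not examined, may say more. This objection stands: the supportable point is that the stated models cannot separate mediator from correlate, not that the plan commits to confusing them.

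**The percentages are power, not error.** The simulated variable truly predicts success, and finding predictors is the declared purpose of Aim 3. This also stands. The 58–98% becomes an error rate only if association is read as mediation. Nor is it the performance of the planned model, which enters age, sex, education and possibly other covariates first and then steps backward through many measures.

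**The count of uncompared mediators.** A reader might conclude that exactly four of the six are never compared between arms. That is too firm. Both the Aim 2 outcomes and the mediators in the aim are introduced as examples, and the SAP does not tie apathy, coping style, motivation or mood to named instruments. If BADS were the mood measure, three would remain off the Aim 2 list. Conversely, mastery and quality of life have no session-4 comparison spelled out either.

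**Importance.** Mediation is one part of the third aim. Hypothesis 3 predicts only associations, and the characteristics it singles out are not change scores. That limits the stakes, but the SAP does set out to examine mediators, and the stated method cannot do so.

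**Conclusion.** The point holds in this form: the SAP announces a mediator analysis but states only a test of association with success. It gives no test of arm on the session-4 change, no indirect effect and no criterion, and it does not say that arm is in the combined model. Aim 2 does not supply the missing step.

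The illustrative size is about 58–98% of trials showing an association for a change untouched by BA-PEP (assumed ORs 1.5–2.2), against about 2–5% when an arm effect is also required. Omitting arm adds a second route to a false lead, at about 17% of trials for an assumed 0.5 SD shift. These figures rest on assumed effects, a single-candidate model and complete session-4 data in 70 patients per arm.

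The change is worth making, but the flaw does not threaten the trial's main conclusions. Aims 1 and 2 are unaffected.

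**What to change.** In the Aim 3 Analysis Plan, replace the mediator sentence with a defined analysis for each of the six variables, naming the instrument:

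- (a) Model the session-4 value on arm, adjusted for that scale's baseline value and the fatigue stratum.
- (b) Model success on the session-4 value, with arm, baseline value and stratum in the model.
- (c) Report the indirect effect, on a stated scale, with a bootstrap interval. Call the variable a mediator only if that interval, or the joint test of (a) and (b), excludes no effect; otherwise call it a correlate of success.

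Label the analysis exploratory. State that it assumes no unmeasured confounding between mediator and outcome, and that it is not adjusted for six tests.

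The cost is SAP wording and about twelve simple models (two for each of six variables) plus bootstraps, on data already planned. The real downside is power: about 42% for step (a) at 0.3 SD, unadjusted, which baseline adjustment would raise somewhat. Some true mediators will therefore be reported only as correlates.
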